## 6.5.1 Description of Activities

#### **Screening and Baseline Assessments:**

Participating physicians will be asked to assess for potential eligibility all sequential patients with Psoriasis for whom a change in treatment regimen is being considered.

Following an explanation of the study by the physician or designee, a written informed consent will be signed by the patients that agree to participate. Subsequent to obtaining written informed consent, potential eligible patients will be assessed for inclusion and exclusion criteria. Those that qualify will be entered in the study cohort. All baseline assessments will be conducted during the baseline / screening visit. The physicians or designee will be required to complete all data on the baseline visit section of the Case report Form using data ascertained by interview or examination of the patient or review of the patient's chart.

There are no laboratory examination requirements for the current study beyond those that are part of routine care. Historical data of up to six months could be used for the baseline values for laboratory tests.

#### Follow-Up Assessments (3, 6, 12, 18 and 24 months):

Given the observational nature of the study there no pre-determined protocol defined requirements for follow up schedules. Physicians will manage the patients in accordance with their current practice, their judgment and regional requirements in the case of reimbursement policies. However, investigators will be encouraged to follow the recommended schedule of assessments for the patients that are enrolled in the study. In addition, all information and data obtained at any visit occurring during the 24 follow up period of the study, including those that are outside of the recommended schedule, will be recorded in the study Case Report Form.

Laboratory tests are not required for the purposes of the study. However, when any tests are conducted as part of routine care or indicated by the condition of the patient, all results should be recorded in the study Case Report Form in physical changes section.

#### **Informed Consent:**

Signed written informed consent will be obtained from all patients prior to conducting any study activities including eligibility assessments. Informed consent may be obtained

from the patient or legally authorized representative.

#### Physical Examination and Medical History:

During the baseline assessment the results of a complete physical examination and medical history will be recorded in the study Case Report Form. For subsequent follow up assessments, only clinically important changes in the Medical History and Physical Examination will be recorded.

#### **Prior and Concomitant Therapy:**

Details of any treatment whether prescription or over the counter used for Psoriasis before and during the study will be recorded in the Case Report Form. These will include dose, frequency and duration of treatment and route.

## **Compliance:**

Compliance with the treatment for Psoriasis will be ascertained by a self administered questionnaire and interview by the treating physician.

#### **Self Administered Questionnaires:**

Patients will be informed about the study requirements with respect to the completion of the self administered questionnaires and will be asked to complete the baseline set of questionnaires while at the physician's office. This will allow the patients to ask any questions and obtain guidance on how the questionnaires are to be completed. Patients will complete the questionnaires and mail them to the data management center, or return them to the treating physicians. During the baseline assessments, patients will be asked to indicate the methods by which they wish to be contacted by the study personnel. The options will be telephone, mail or e-mail. As part of the written informed consent patients will be asked to explicitly agree to be contacted using these methods for the purposes of the study and will be asked to provide their contact coordinates.

Patients will be identified only through the randomly generated study patient ID number.

Any identifying information will never be included on any questionnaire. If the patient chooses to mail-in or complete the questionnaire at the investigator sites, the return envelop will include only the patient ID and no other identifying data. Only the study coordinators will have access to patient information that will be use to follow up for non-responders.

#### Physician and Patient Recruitment and Retention:

Given the observational nature of the study one of the most important challenges will be patient retention and minimization of loss to follow up. The project manager will monitor patient follow up in the study.

#### **Patient Discontinuation from the Study:**

Patients could be withdrawn from the study at any time by the treating physician or on their own accord. Patients that participate in another trial will be withdrawn from the study. Patients that terminate treatment or switch from their current treatment will be followed for the 24 month study follow up period. Patients may change treatment at the discretion of the physician including switching from one of the defined treatment cohorts to another. Lack of therapeutic response, low compliance to treatment or the incidence of adverse events will not necessitate study withdrawal.

# 6.5.2 Product Supply:

In the current study patients will be treated with topical agents, traditional systemic agents and adalimumab as monotherapy or in combination. As an observational study all treatments will be accessed as per routine customary practice in the region. More specifically, AbbVieE will not supply or reimburse for any treatment used by the patients in the study. Patients will be prescribed the medications by the treating physician and will acquire these through the available insurance plan / government reimbursement or purchase with their own funds. All medications will be used in accordance to the current marketing label, the product monograph and regional requirements.

#### 7.0 Adverse Events

The primary aim of the current PMOS is to assess real life effectiveness. Given that the primary objective is not to assess any safety parameters only spontaneously reported Serious Adverse Events (SAEs), unusual failure in efficacy and Pregnancies must be reported.

# 7.1 Adverse Event Definition and Serious Adverse Event Categories

An adverse event (AE) is defined as any untoward medical occurrence in a patient, which does not necessarily have a causal relationship with their treatment. An adverse event can therefore be any unfavorable and unintended sign (including an abnormal laboratory finding), symptom, or disease temporally associated with the use of a medicinal product, whether or not the event is considered causally related to the use of the product.

Such an event can result from use of the drug as stipulated in the labeling, as well as from accidental or intentional overdose, drug abuse, or drug withdrawal. Any worsening of a pre-existing condition or illness is considered an adverse event.

If an adverse event meets any of the following criteria, it is considered a **serious adverse** event (SAE):

**Death of Subject** An event that results in the death of a subject.

**Life-Threatening** An event that, in the opinion of the investigator, would have resulted in immediate fatality if medical intervention had not been taken. This does not include an event that would have been fatal if it had occurred in a more severe form.

Hospitalization An event that results in an admission to the hospital for any length of

time. This does not include an emergency room visit or admission to an outpatient facility.

**Prolongation of Hospitalization** An event that occurs while the study subject is hospitalized and prolongs the subject's hospital stay.

**Congenital Anomaly** An anomaly detected at or after birth or any anomaly those results in fetal loss.

**Persistent or Significant Disability/Incapacity** An event that results in a condition that substantially interferes with the activities of daily living of a study subject. Disability is not intended to include experiences of relatively minor medical significance such as headache, nausea, vomiting, diarrhea, influenza and accidental trauma (*e.g.*, sprained ankle).

Important Medical Event Requiring Medical or Surgical Intervention to Prevent Serious Outcome An important medical event that may not be immediately lifethreatening or result in death or hospitalization, but based on medical judgment may jeopardize the subject and may require medical or surgical intervention to prevent any of the outcomes listed above (*i.e.*, death of subject, life-threatening, hospitalization, prolongation of hospitalization, congenital anomaly, or persistent or significant disability/incapacity). Examples of such events include allergic bronchospasm requiring intensive treatment in an emergency room or at home, blood dyscrasias or convulsions that do not result in inpatient hospitalization, or the development of drug dependency or drug abuse.

Spontaneous Abortion Miscarriage experienced by study subject.

Elective Abortion Elective abortion performed on study subject.

## 7.2 Severity

The physician will use the following definitions to rate the severity for any adverse event being collected as an endpoint/data point in the study and for all serious adverse events.

Mild The adverse event is transient and easily tolerated by the subject.

Moderate The adverse event causes the subject discomfort and interrupts the subject's usual activities.

Severe The adverse event causes considerable interference with the subject's usual activities and may be incapacitating or life-threatening.

## 7.3 Relationship to Pharmaceutical Product

The physician will use the following definitions for any adverse event being collected as an endpoint/data point in the study and for all serious adverse events, to assess the relationship of the adverse event to the use of the pharmaceutical product:

Probably Related An adverse event has a strong temporal relationship to study drug or recurs on re-challenge and another etiology is unlikely or significantly less likely.

**Possibly Related** An adverse event has a strong temporal relationship to the study drug and an alternative etiology is equally or less likely compared to the potential relationship to study drug.

Probably Not Related An adverse event has little or no temporal relationship to the study drug and/or a more likely alternative etiology exists.

**Not Related** An adverse event is due to an underlying or concurrent illness or effect of another drug and is not related to the study drug (*e.g.*, has no temporal relationship to study drug or has a much more likely alternative etiology).

If an investigator's opinion of possibly, probably not, or not related to pharmaceutical product is given, an alternate etiology must be provided by the investigator for the adverse event.

#### 7.4 Serious Adverse Event Collection Period

Serious adverse events will be reported to AbbVie from the time the physician obtains the patient's authorization to use and disclose information (or the patient's informed consent) until 30 days or 5 half-lives following the intake of the last dose of physician-prescribed treatment.

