site including redness, itching, bruising, pain or swelling, stomach pain, nausea, headache and back pain. Rare side effects include malignancies, reversible lupus (without renal or CNS complications) and cytopenias. Therefore all patients treated with anti-TNF alpha agents must be monitored for serious infections and particularly tuberculosis before, during and after treatment. In addition monitoring of liver function, CBC and hepatitis profile are recommended.

The efficacy of adalimumab in controlling the symptoms of psoriasis has been demonstrated in several controlled clinical trials. Taken collectively the results of these studies that have been conducted on over 1600 patients with moderate to severe chronic plaque psoriasis who were candidates for systemic therapy or phototherapy have shown that adalimumab is efficacious in controlling the symptoms of psoriasis and in improving the quality of life of patients. More specifically, when compared to placebo or methotrexate, patients treated with adalimumab had a significantly higher therapeutic response rate, defined as achieving a PASI 75 and a Physician Global Assessment (PGA) value of  $\leq 1$  (indicating clear or minimal disease) at 16 weeks. The magnitude of effect versus placebo ranges from four-fold (79.6% versus 18.9%) to ten-fold (70.9% versus 6.5%) for PASI 75 and from 2.5 times (73.1% versus 30%) to 14.5 times (62.2% versus 4.3%) for PGA of clear or minimal. When compared to methotrexate the magnitude of effect is 2.2 times for PASI 75 (79.6% versus 35.5%) and 2.5 times for PGA of "clear or minimal" (73.1% versus 30%) 1.11-18,22-29. In addition, in one clinical trial patients crossed over to placebo after 33 weeks of treatment with adalimumab were significantly more likely to lose therapeutic response when compared to patients that were maintained on adalimumab up to week 52. With respect to quality of life, when compared to patients treated with placebo or methotrexate those treated with adalimumab in these controlled clinical trials have had better improvement in the Dermatology Quality of Life Index (DLQI) total score as well as in the disease severity, pain and pruritus subscales. Better improvement in the Physical and Mental subscales of the Medical Outcomes Study Short Form 12 (SF-12) was also observed for the adalimumab treated patients when compared

to placebo.

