## 6.4 Study Duration

All patients will be followed for 24 months. Given the observational nature of the study there will be no pre-defined protocol driven assessments and physician visits could take place according to the routine practice or the judgment of the treating physician. However, assessments at 3, 6, 12, 18 and 24 months after baseline will be recommended and encouraged given that this is within the acceptable practice patterns for patients undergoing treatment for moderate to severe psoriasis. In certain cases patients may be assessed more frequently than what will be recommended. Physicians will be asked to record in the Case Report Forms data from all visits occurring during the study period.

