In order to better assess the impact of the treatment received and changes in the regimen the treatment will be handled as a time – dependent covariate in these analyses.

With respect to achieving therapeutic response end points and incidence of articular and extra-articular manifestations between group differences will be assessed with multivariate logistic regression while Cox proportional hazard models will be used to assess between group differences with respect to the time of achieving therapeutic response and first occurrence of articular and extra-articular manifestations.

Descriptive statistics will be used to assess the between group and regional differences with respect to patient characteristics and disease parameters. Descriptive statistics will also be used to assess the practice patterns of Canadian dermatologists in the management of patients with moderate to severe PLAQUE PS. The study cohorts will be divided into Canadian regions as Quebec, Ontario, Maritimes and Western Canada.

Underdiagnosis of articular and extra articular manifestations will be assessed by the prevalence of existing articular manifestations and a survey of participating physicians with respect to their estimates of the prevalence of articular and extra- articular manifestations in the patients.

Safety will be assessed by the incidence of treatment emergent adverse events with adjusted relative risks used to compare the three treatment groups.

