### 2.10.2 Safety Measures

Safety and tolerability will be assessed with the incidence of treatment-emergent adverse events. Incidence of treatment emergent serious adverse events will be recorded by the treating physician through the 24 months of treatment. Severity of the adverse event and causal relation to the treatment will be assessed by the treating physician. All adverse events will be coded as per the MedDRA dictionary of terms.

i. All serious adverse events will be recorded and reported as per regional regulatory guidelines and requirements.

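### SAE reporting is tied to the last dose, follow-up runs to month 24, and the cohorts are compared on incidence with no person-time, so the SAE collection period needs one definition

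*Protocol*

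**What the plan says.** Protocol 7.4, headed as the SAE collection period, has SAEs reported to the sponsor from consent or authorization "until 30 days or 5 half-lives following the intake of the last dose of physician-prescribed treatment". It gives no rule for choosing between the two limits. It also does not say whether, after a switch, the last dose is that of the cohort-defining agent or of whatever is prescribed next.

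Follow-up is longer. Protocol 6.4 states: "All patients will be followed for 24 months". Protocol 6.5.1 adds: "Patients that terminate treatment or switch from their current treatment will be followed for the 24 month study follow up period".

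SAP 2.10.2 uses another period: "Incidence of treatment emergent serious adverse events will be recorded by the treating physician through the 24 months of treatment". It defines neither treatment-emergent nor a limit after the last dose. It then says: "All serious adverse events will be recorded and reported as per regional regulatory guidelines and requirements", again with no end date.

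The comparison is set in Protocol 10.2: "Safety will be assessed by the incidence of treatment emergent adverse events with adjusted relative risks used to compare the three treatment groups". No person-time denominator is named there or in SAP 2.10.2.

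**The concern.** A site cannot tell from these sections when to stop collecting SAEs, and a programmer cannot tell which SAEs to count. The sections pull apart most for a patient who stops all prescribed treatment early and keeps attending. Visits continue to month 24, but the only explicit SAE cut-off in the protocol closes soon after the last dose.

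Two things are at stake. First, Protocol 5.2 makes ongoing safety assessment of all three treatment types a secondary objective, and Protocol 4.0 wants emerging signals detected. Later-onset events are the ones a short post-dose window can miss. Second, a relative risk of incidence treats patients as if they were observed for equal time. If cohorts differ in how often patients stop all treatment, or if sites apply the 30-day limit in one cohort and the half-life limit in another, observed time differs and the ratio shifts even when the true SAE rates are equal.

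**Working it through.** The plan states no figure to reproduce here. The check is arithmetic on the plan's own periods.

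**Inputs**
- Follow-up: 24 months (Protocol 6.4).
- Days per month: 30.4 (SAP 3.7), so follow-up is 24 × 30.4 = 729.6 days.
- Post-dose window *w*: 30 days (Protocol 7.4). The documents give no half-life, so *w* = 5, 70 and 100 days are assumptions standing in for the five-half-life limit.

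**Gap for a patient who stops all prescribed treatment at month *m***
- Days remaining = 729.6 − 30.4*m*
- Days outside the window = days remaining − *w* (not below 0)
- Share = days outside ÷ days remaining

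Results for *w* = 30 days:

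| Stop month | Days remaining | Days outside | Months outside | Share of remaining |
|---|---|---|---|---|
| 3 | 638.4 | 608.4 | 20.0 | 95.3% |
| 6 | 547.2 | 517.2 | 17.0 | 94.5% |
| 12 | 364.8 | 334.8 | 11.0 | 91.8% |
| 18 | 182.4 | 152.4 | 5.0 | 83.6% |
| 22 | 60.8 | 30.8 | 1.0 | 50.7% |
| 23 | 30.4 | 0.4 | 0.0 | 1.3% |

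With an assumed *w* = 70 days, the share is 87.2% for stopping at month 6 and 80.8% at month 12. With an assumed *w* = 100 days, it is 81.7% and 72.6%.

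**When is most of the remaining time outside the window?** When the patient stops before month (729.6 − 2*w*) ÷ 30.4. That is month 22.0 for 30 days, and 23.7, 19.4 and 17.4 for the assumed 5, 70 and 100 days.

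**Patients who switch.** The window in 7.4 runs from the last dose of prescribed treatment. On that wording, a patient who moves to another prescribed agent and stays on it to month 24 has a gap of 0%.

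**Effect on the comparison (illustration only).** Every input in this step is assumed: an SAE rate of 0.04 per year in all cohorts, stoppers leaving all treatment at month 6, and the 30-day limit.
- Observed incidence, full 24 months: 1 − exp(−0.04 × 2) = 7.69%.
- Observed incidence, stoppers seen to month 7: 1 − exp(−0.04 × 7/12) = 2.31%.
- Cohort with 10% stoppers: 0.9 × 7.69 + 0.1 × 2.31 = 7.15%.
- Cohort with 20% stoppers: 6.61%. Cohort with 40% stoppers: 5.54%.
- Ratio of the 10% cohort to the others: 7.15/6.61 = 1.08 and 7.15/5.54 = 1.29.
- If the stopping rates are exchanged between cohorts, the ratios become 0.92 and 0.77.

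The bias can therefore run either way, and the documents give no stopping rates by cohort to settle which.

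**The case against.** The best reply is that these sections govern different things. Protocol 6.5.1 sets how long patients are followed and says nothing about SAEs. The SAP counts treatment-emergent events, and such a count can have a post-dose cut-off beside longer effectiveness follow-up. This stands in part: a reader might infer three contradictory rules for SAE collection, and that is too strong. What remains is a cut-off with no selection rule in one document, a 24-month period with no cut-off in the other, and key terms left undefined.

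A second reply is that 7.4 limits only reporting to the sponsor, and that other routes stay open to month 24. SAP 2.10.2 says all SAEs are recorded. Protocol 6.5 asks for all management information over 24 months. Protocol 5.3.2 and 6.5.1 record changes in medical history. A reader might infer that SAEs off treatment are certainly lost, and the documents do not establish that. But these protocol routes are not SAE rules. Table 1 has no adverse-event row, the CRF sections listed in Protocol 9.0 include none for adverse events, and that section restricts collection to data the protocol specifies. Protocol 7.0 requires only spontaneously reported SAEs. Section 7.4 is still the only explicit cut-off a site has.

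Third, safety is not the primary aim, and SAP 3.7 already derives months of exposure by treatment class. Both are true. The plan does not commit to using that exposure as a denominator, and exposure is not the same as time under SAE observation.

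Two further inferences go too far. The introduction says patients on anti-TNF agents "must be monitored for serious infections and particularly tuberculosis before, during and after treatment". That sentence is about serious infections. Malignancy is listed separately as a rare side effect, and the sentence is clinical background rather than a data-collection rule. Nor is the window endless for a patient still treated at month 24, because Protocol 6.0 caps follow-up at 24 months.

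**Conclusion.** The point holds in a limited form. Protocol 7.4 and SAP 2.10.2 do not yield one SAE collection period, and 7.4 permits non-collection in most of the attended follow-up of a patient who stops all prescribed treatment. On the 30-day reading the gap is about 20, 17 or 11 of the 24 months for stopping at month 3, 6 or 12. Patients who switch and remain treated are covered on the literal wording. They would fall outside only if last dose meant that of the cohort-defining agent, which the text leaves open.

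A reader might infer that SAE-observed time is known to differ between cohorts, or that the adalimumab comparison is biased by a stated amount. Neither follows. With no person-time denominator, Protocol 10.2 is exposed to any such difference, but the documents give no half-lives, SAE rates or stopping rates. Size and direction cannot be computed, and the ratios above only show the mechanism. A related asymmetry is on the page: Protocol 7.5 states the 24-hour notification duty only for patients using a sponsor product.

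This should be corrected. It affects a secondary objective and leaves the primary effectiveness analysis untouched.

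**What to change.** Reconcile Protocol 7.4 and SAP 2.10.2 as follows:
1. Use one SAE collection period for all three cohorts: from consent to the month-24 or withdrawal visit, plus a single stated post-dose tail whose length follows one written rule.
2. Define last dose after a switch, saying whether it refers to the cohort-defining agent or to any prescribed psoriasis treatment. Define treatment-emergent by reference to it.
3. Flag each SAE as on-treatment or post-treatment, so that the treatment-emergent count can still be produced.
4. Report SAEs per patient-year of SAE observation, by cohort, beside the adjusted relative risk in Protocol 10.2.

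The cost is wording in two documents, one derived flag and one denominator. No visits are added, because patients who stop are already followed to month 24. The downside is some extra SAE forms from patients off treatment. None of this changes patient management.
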